6. ANALYSIS FOR OTHER STUDY OUTCOME MEASURES

6.1 Primary indications for platelet transfusion

We will present the primary indications for platelet transfusion. The indications reported under 'other indications' will be categorized where possible at the discretion of the primary investigators and will be reported.

6.2 Transfusion volume, duration and infusion rate

Transfusion infusion rates will be calculated by dividing the volume (mL/kg) by the transfusion duration (in hours). Transfusion infusion rates will be presented in two bubble plots, separately for platelet transfusions given based on platelet count threshold and platelets transfusion given for active bleeding, prevention of major bleeding, lumbar puncture, surgical procedure and any other primary indications.

6.3 Platelet count prior to transfusion

We collected the last platelet count measured prior to platelet transfusion, if available within maximum 24 hours before transfusion.

The available platelet count values prior to transfusion will be presented in two box plots, separately for the platelet transfusions given based on platelet count threshold and platelets transfusion given for active bleeding, prevention of major bleeding, lumbar puncture, surgical procedure and any other primary indications.

We will present the proportion of platelet counts prior to transfusions given based on threshold that is below the restrictive threshold ($<25 \times 10^9/L$), between the restrictive and below the liberal threshold ($25 \times 10^9/L$), and above the liberal threshold ($\ge 50 \times 10^9/L$) as compared in the PlaNeT2-Matisse trial. (1)

6.4 Platelet transfusion increment

We also collected the post-transfusion platelet count at the most recent measurement after the platelet transfusion, if available within maximum 24 hours after transfusion. All platelet transfusions given based on platelet count threshold in which both pretransfusion and post-transfusion platelet count are available will be used for the following plots. Transfusion increment will be calculated by subtracting post-transfusion platelet count from pre-transfusion platelet count.

Transfusion increments will be plotted separately for the different transfusion volume categories as well as for all transfusions. Transfusion increment of a transfusion volume group will not be plotted if 5 or less platelet transfusions given at this volume.

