2.2 Other study outcome measures

- 4. Primary indications for platelet transfusion
- 5. Volume, duration and infusion rate of platelet transfusion
- 6. Platelet count prior to platelet transfusion
- 7. Platelet transfusion increment, stratified for transfusion volume
- 8. Transfusion related adverse effects

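### SAP section 6.4 defines the platelet increment as pre-transfusion minus post-transfusion count, which reverses the sign of descriptive outcome 7

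*SAP*

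**What the plan says.** SAP section 2.2 lists outcome 7 by name only: "Platelet transfusion increment, stratified for transfusion volume". The formula appears once, in section 6.4: "Transfusion increment will be calculated by subtracting post-transfusion platelet count from pre-transfusion platelet count".

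The two counts that enter it are described in separate places:

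- Pre-transfusion count (section 6.3): "We collected the last platelet count measured prior to platelet transfusion, if available within maximum 24 hours before transfusion".
- Post-transfusion count (section 6.4): "We also collected the post-transfusion platelet count at the most recent measurement after the platelet transfusion, if available within maximum 24 hours after transfusion".

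Section 6.4 also sets the analysed pairs for its plots: "All platelet transfusions given based on platelet count threshold in which both pretransfusion and post-transfusion platelet count are available will be used for the following". The increments are then plotted overall and by transfusion volume category, and a volume category with five or fewer transfusions is left out. The missing-data table in section 4.2 repeats the two 24-hour limits and says nothing about how the difference is formed.

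**The concern.** To subtract B from A is to compute A − B. Section 6.4 therefore instructs the analyst to compute pre minus post, and that contradicts the name of the quantity, because an increment is an increase. A programmer who follows the sentence would produce plots in which counts appear to fall after transfusions that raised them. If larger volumes produce larger rises (an assumption, since the SAP gives no data on this), the plots by volume would also appear to run the wrong way.

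The matter is worth settling even if the analyst would spot it. Section 7 says the SAP will be published in a registry. If the code follows the text, the sign of the reported outcome is wrong. If the code silently uses the opposite difference, the published plan does not describe the analysis that was done.

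**Working it through.** The SAP states no numerical increment, so there is no figure of its own to reproduce. The check is of sign only.

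**Inputs.** Pre = the last count within 24 hours before the transfusion (section 6.3). Post = the recorded count within 24 hours after it (section 6.4). The example counts below are assumed for illustration and do not come from the SAP.

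**Formulas.**

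- As written in section 6.4: W = pre − post.
- Increment in the ordinary sense: D = post − pre.
- Relation: W = −D for every pair.

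**Numbers (×10^9/L).**

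| Assumed pair | As written, pre − post | Increment, post − pre |
|---|---|---|
| Rise, 20 to 70 | 20 − 70 = −50 | 70 − 20 = +50 |
| Fall, 20 to 15 | 20 − 15 = +5 | 15 − 20 = −5 |
| No change, 20 to 20 | 0 | 0 |

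**What follows for the plots.** Because W = −D, the absolute size of each value is unchanged. A group's median changes sign. Its lower quartile as written is minus the true upper quartile, and the reverse, so the interquartile width is unchanged. Each plot is reflected about zero and loses no information.

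**Does another part of the SAP correct it?**

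- Section 2.2 gives the name without a formula.
- Sections 4.2 and 6.3 say when counts are recorded.
- No section mentions an absolute value, a decrement or a reversed axis.
- The sentence in section 6.4 is complete, so damage in text extraction does not explain it.

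**Does the error spread?** The main outcomes in section 2.1 are the transfusion day prevalence rate, its case-mix adjusted version and the 28-day cumulative incidence. Sections 5.1 to 5.3 define them from transfusion days, admission days, covariates and time to first transfusion. None uses the increment. Nor do the analyses of indication, infusion rate, pre-transfusion count or adverse effects in sections 6.1 to 6.3 and 6.5.

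**The case against.** The strongest reply is that this is a slip of wording with little consequence. The name of the outcome shows which direction was meant. The quantity is descriptive, is not a main outcome, and enters no test, model or decision rule. An analyst would notice if almost all increments came out negative. All of this stands, and it is why the point is not a critical one. It does not make the sentence right: it is the whole operational definition of a listed outcome, and no other text overrides it.

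A reader might also infer something stronger: that a further platelet transfusion given before the post-transfusion count distorts the relation between volume and increment, perhaps doubling the value credited to the first transfusion. Section 6.4 has no exclusion for such pairs, and section 5.1 allows more than one transfusion in a day, so they are possible. The SAP does not support going further, for these reasons:

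- The post-transfusion value is not any count in the window. It is the "post-transfusion platelet count at the most recent measurement after the platelet transfusion". That phrase could mean the count closest to the transfusion or the last one within 24 hours. Under the first meaning, intervening transfusions would be less frequent.
- The SAP gives no frequency for such pairs, so neither the distortion nor the number lost by excluding them can be sized.
- A doubling would need the second transfusion to have the same effect as the first and no decline in the count between them. Both are assumptions.
- Data collection ended in August 2023 (section 1), and the SAP describes one post-transfusion count per transfusion. Choosing a different count may therefore be impossible.

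The missing exclusion is a possible refinement of a descriptive plot. It is not an error in the text.

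**Conclusion.** Section 6.4 is wrong as written. Followed exactly, it reverses the sign of every non-zero increment in outcome 7, and pairs with no change stay at zero. The finding rests only on the plain meaning of the sentence and on the absence of any correcting text elsewhere in the SAP.

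The effect is confined to the direction of the increment plots for threshold-based transfusions with both counts available. Magnitudes, the three main outcomes and all other analyses are unaffected. This is a minor to moderate correction. A reader might conclude that the study's estimates of platelet use, or the size of the response to transfusion, are in doubt. The document does not support that, because the difference is a pure change of sign and no other analysis uses it.

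**What to change.** Replace the sentence in section 6.4 with one stating that the increment equals the post-transfusion platelet count minus the pre-transfusion platelet count, so that a positive value means a rise. Check that the plotting code uses the same difference and that the axis label says so. This takes one line of text and at most one line of code. It needs no new data and loses no pairs.

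Optionally, and only where the recorded times are precise enough to order the events, flag or exclude pairs in which another platelet transfusion was given between the index transfusion and the post-transfusion count. This would cost an unknown number of pairs, so the number flagged or excluded should be reported. If the times do not allow it, a sentence noting the limitation is enough.

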6.5 Transfusion related adverse effects following platelet transfusion

In the absence of clear definitions of transfusion-associated side effects in preterm infants, local investigators were asked to register any perceived transfusion-associated adverse effects if they consider the adverse event to be potentially associated with the preceding transfusion.

We will report the percentage of platelet transfusions for which an adverse events was registered and the mean/median time between occurrence of the adverse effect and the platelet transfusion, in days. The observed adverse effects will be categorized where possible at the discretion of the primary investigators and will be reported in text.

7. GENERAL REMARKS

Reporting guidelines

The study results will be presented according to the recommendations of the STROBE guidelines.

Publication

The statistical analysis plan will be published in the ISRCTN registry.

